- Once the MTD for DAC/THU has been identified, the MTD dose level will be expanded by 4 patients to confirm its safety. Then, including these 10 patients at the MTD, a total of 10 NSCLC patients with high (50% or greater) intratumoral PD-L1 expression and 10 NSCLC patients with low (0-49%) intratumoral PL-L1 expression will be accrued to the first stage of each of two separate Phase II cohorts using individual Simon optimal designs. If 5 or more patients of the 10 first stage NSCLC patients in the high PD-L1 cohort respond to treatment, the cohort will be expanded to 23 patients. If 11 of 23 of these patients respond to treatment, the trial will be deemed positive for NSCLC with high PD-L1 expression. If 2 or more of the 10 first stage NSCLC patients in the low PD-L1 expression cohort respond to treatment, the cohort will be expanded to 29 patients. If 6 or more of these 29 patients experience a response, the trial will be deemed positive for NSCLC with low PD-L1 expression. Up to 10 EsC patients, including those considered to be part of the Phase I component after the MTD has been identified, will be enrolled into a separate cohort to examine responses to DAC-THU/pembrolizumab at the MTD. If 2 or more of these 10 EsC patients respond to treatment, these findings may warrant an amendment or a separate Phase II trial to determine response rates to DAC-THU/pembrolizumab in EsC patients. Similarly, if 2 or more of 10 MPM patients respond to treatment, these findings may warrant an amendment or a separate Phase II trial to determine response rates to DAC-THU/pembrolizumab in MPM.
- Biopsies of index lesions will be obtained at baseline and at treatment evaluation following the first course of therapy for analysis of pharmacodynamic endpoints.
- Patients will be followed for toxicity for at least 30 days after treatment has been discontinued, start of new anti-cancer treatment or until death, whichever occurs first.

TABLE OF CONTENTS

PRÉ	ECIS		2
TAF	BLE OF	F CONTENTS	5
STA	TEME	NT of COMPLIANCE	10
1	INTRO	DDUCTION	10
1.1	Study	v Objectives	10
	1.1.1	Primary Objectives	10
	1.1.2	Secondary Objectives	10
1.2	Backg 1.2.1	ground and Rationale Background and Significance:	
	1.2.2 Oral A	Pharmacokinetics of DAC Alone Following Intravenous (IV), Subcutaneous (SC administration in Non-Human Primates) and 18
	1.2.3 Bioava	Identification of Dose and Timing of Oral THU Required to Increase ailability of DAC in Non-Human Primates	

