Pembrolizumab is a potent and highly selective humanized monoclonal antibody (mAb) of the IgG4/kappa isotype which directly inhibits interaction of PD-1 with its ligands, PD-L1 and PD-L2 (20). In 2015, pembrolizumab was approved in the US for second-line therapy of NSCLC (93), and in 2016, this immune checkpoint inhibitor was approved as first-line therapy for NSCLC with high level (> 50%) PD-L1 expression. In 2017, the FDA approved pembrolizumab for recurrent locally advanced, or metastatic gastroesophageal cancer with PD-L1 expression (CPS) greater than or equal to 1. In a Phase I trial (Keynote 001), 495 patients with advanced NSCLC were assigned to either training or validation groups, and received pembrolizumab at 2 mg/kg or 10 mg/kg every three weeks, or 10 mg/kg every two weeks (94). Fatigue, decreased appetite and pruritus were the most common side effects (single digit numbers); severe pneumonitis was observed in 1.8% of patients, including one death. The ORR, median PFS and median OS for treatment naïve patients were 24.8%, 6.0 months and 16.2 months, respectively, vs 18%, 3.0 months, and 9.3 months, respectively, for previously treated patients. Subsequent analysis demonstrated ORR and median PFS of 43.9% and 6.1 months vs 50.0% and 12.5 months, respectively, for treatment naïve and previously treated patients whose tumors had a proportion score (PS) of at least 50% cancer cells showing positive membrane staining for PD-L1 (94).

In a Phase III trial (Keynote 024), Reck et al (95) randomly assigned 305 patients with untreated, advanced NSCLC with no sensitizing EGFR or ALK mutations and PD-L1 expression on 50% or more tumors cells to receive either pembrolizumab (200 mg Q3W) or platinum-based chemotherapy. Cross-over from the chemotherapy to pembrolizumab was allowed. The objective response rate was 44.8% in the pembrolizumab arm compared to 27.8% in the chemotherapy arm. Median progression free survival was 10.3 months (95% CI: 6.7 months to not reached) compared to 6.0 months (95% CI: 4.2 to 6.2 months) in the chemotherapy arm. Median duration of response was longer (not reached; range 1.9 to 14.5 months) in the pembrolizumab arm compared to 6.3 months (range: 2.1 to 12.6 months). Grade 3, 4, or 5 treatment related adverse events were significantly lower in the pembrolizumab arm compared to the chemotherapy arm (26.6% vs 53.3%).

Adverse Event		umab Group = 154)	Chemotherapy Group (N=150)		

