2 ELIGIBILITY ASSESSMENTAND ENROLLMENT

2.1 ELIGIBILITY CRITERIA

2.1.1 Inclusion Criteria

- 2.1.1.1 Histologically or cytologically confirmed, inoperable or unresectable locally advanced, or metastatic NSCLC, esophageal cancers including Seiwert-Stein Type I and Type II gastro-esophageal junction (GEJ) carcinomas, or MPM.
- 2.1.1.2 NSCLC patients with no prior systemic treatment, or those with prior first line treatment including an immune checkpoint inhibitor, are eligible for study.
- 2.1.1.3 Patients with esophageal and gastro-esophageal junction (GEJ) cancers are potentially eligible for study if they have received or refused first line standard of care cytotoxic therapy, and subsequent targeted therapy if appropriate.
- 2.1.1.4 Patients with MPM are eligible for study if they have received, refused or are ineligible for first line chemotherapy.
- 2.1.1.5 Patients who received DNA demethylating agents or PD-1/PD-L1 inhibitors for another malignancy may be eligible for study if there were no dose-limiting immune related events, and there has been either no clinical evidence of disease or minimal residual disease that has been stable for at least three years.
- 2.1.1.6 Patients must have analysis of PD-L1 expression in cancer cells quantitated by immunohistochemistry analysis.
- 2.1.1.6.1 Patients in Cohort 1 (Dose Escalation) may have any level of expression.
- 2.1.1.6.2 Patients in Cohort 2 (Dose Expansion: NSCLC with high PD-L1) must have \geq 50% expression in cancer cells.
- 2.1.1.6.3 Patients in Cohort 3 (Dose Expansion: NSCLC with low PD-L1) must have 0-49% expression. Note: Patients in this cohort must have been offered and refused standard of care platinum-based chemotherapy.
- 2.1.1.6.4 Patients in Cohort 4 (Dose Expansion: EsC) may have any level of expression.
- 2.1.1.6.5 Patients in Cohort 5 (Dose Expansion: MPM) may have any level of expression.
- 2.1.1.7 Measurable disease, per RECIST 1.1. (see Section **6.3.3** for the evaluation of measurable disease).
- 2.1.1.8 Willingness to undergo tumor biopsies if safely accessible per PI discretion before and after treatment.
- 2.1.1.9 Age ≥18 years. Because no dosing or adverse event data are currently available on the use of Decitabine (DAC) and Tetrahydrouridine (THU) in combination with Pembrolizumab in patients < 18 years of age, children are excluded from this study, but will be eligible for future pediatric trials.

- 2.1.1.10 ECOG performance status of ≤ 2 (see **Appendix 1**).

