Since published data have demonstrated a response rate of 45% for first-line pembrolizumab alone in NSCLC patients with PD-L1 expression of 50% or greater (95), (98), this trial will try to demonstrate if a response rate in excess of 45% may be realized in NSCLC patients with \geq 50% PD-L1 expression by the addition of DAC/THU. Briefly, NSCLC patients with high intratumoral (50% or greater) PD-L1 expression will be evaluated for response as part of a Simon optimal twostage Phase II trial design (116) in order to rule out an unacceptably low PR+CR rate of 35% (p0=0.35) in favor of an improved response rate of 60% (p1=0.60). With alpha=0.10 (probability of accepting a poor treatment=0.10) and beta=0.20 (probability of rejecting a good treatment=0.20), the first stage will determine the response rate in 10 evaluable patients, including those NSCLC patients among the 10 who are treated at the MTD from the Phase I cohort who have high intra-tumoral PD-L1 expression. If 0 to 4 of the 10 patients have a clinical response, then no further patients will be accrued. If 5 or more of these 10 patients have a response, then accrual would continue until a total of 23 evaluable patients have been treated at the MTD. As it may take up to several months to determine if a patient has experienced a response, a temporary pause in the accrual may be necessary to ensure that enrollment to the second stage is warranted. If there are 5 to 10 patients with a response out of 23 patients, this would be an uninterestingly low response rate. If there were 11 or more of 23 (47.8%) who experienced a response, this would be sufficiently interesting to warrant further study in later trials. Under the null hypothesis (35% response rate), the probability of early termination is 75.2%.

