10.1 METHODS OF ANALYSIS

Response rates will be calculated as the percent of patients whose best response is a CR or PR. Toxicity information recorded will include the type, severity, time of onset, time of resolution, and the probable association with the study regimen. Tables will be constructed to summarize the observed incidence by severity and type of toxicity.

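### High PD-L1 NSCLC cohort: the stated aim is a response rate above 45%, but the two-stage rule tests 35%, and its minimum success of 11/23 does not rule out 45%

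*Combined protocol and SAP*

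**What the plan says.** Section 10 (Statistical Considerations) cites a 45% response rate for first-line pembrolizumab alone in NSCLC with PD-L1 of 50% or more, and then states that "this trial will try to demonstrate if a response rate in excess of 45% may be realized in NSCLC patients" in this PD-L1 group when DAC-THU is added. The following sentence sets up a Simon optimal two-stage design to "rule out an unacceptably low PR+CR rate of 35% (p0=0.35) in favor of an improved response rate of 60% (p1=0.60", with alpha 0.10 and beta 0.20. Accrual stops if 4 or fewer of the first 10 respond. Otherwise the cohort goes to 23, and 11 or more responders is the success criterion, of which Section 10 says "this would be sufficiently interesting to warrant further study in later trials".

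The précis puts the same criterion more strongly: "If 11 of 23 of these patients respond to treatment, the trial will be deemed positive for NSCLC with high PD-L1 expression".

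The benchmark comes from Section 1.2.10. For the randomised first-line trial it reports: "The objective response rate was 44.8% in the pembrolizumab arm compared to 27.8% in the chemotherapy arm". For an earlier single-agent trial it gives, in untreated and previously treated patients respectively with PD-L1 of at least 50%, "ORR and median PFS of 43.9% and 6.1 months vs 50.0% and 12.5 months, respectively".

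On eligibility, Section 2.1.1 says: "NSCLC patients with no prior systemic treatment, or those with prior first line treatment including an immune checkpoint inhibitor, are eligible for study". On analysis, Section 10.1 says: "Response rates will be calculated as the percent of patients whose best response is a CR or PR". It plans no interval.

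**The concern.** Two adjacent sentences of Section 10 carry different reference rates: the aim is to exceed 45%, and the null is 35%. The stated alpha of 0.10 is the chance of a positive result when the true rate is 35%. It says nothing about the chance of a positive result when the regimen does no better than pembrolizumab alone at 45%.

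The cohort is single-arm, so the null rate alone gives a positive result its meaning. A reader who takes the 45% aim from Section 10 and the positive label from the précis would conclude that 11/23 (47.8%) shows benefit over pembrolizumab alone. The rule does not support that conclusion. Because only a percentage is to be reported, the planned analysis would not show the gap either.

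**Working it through.** **Inputs.** From Section 10: p0 = 0.35, p1 = 0.60, alpha = 0.10, beta = 0.20; stop if 4 or fewer of 10 respond; success if 11 or more of 23; stated early termination of 75.2% at 35%. From Section 1.2.10: pembrolizumab-alone rates of 43.9% (untreated), 44.8% (first-line randomised trial) and 50.0% (previously treated). Section 10 rounds the benchmark to 45%. The 40% row below is my assumption. It is shown because checkpoint-pretreated patients are eligible and the documents I could read give no rate for them.

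**Formulas.** With x₁ responders among the first 10 and X₂ among the next 13:

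- P(stop at stage 1) = P(Bin(10, p) ≤ 4).
- P(positive) = Σ over x₁ = 5 to 10 of P(Bin(10, p) = x₁) × P(Bin(13, p) ≥ 11 − x₁).

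**Reproducing the plan.** At p = 0.35, P(stop) = 0.7515, against the stated 75.2%. The terms of P(positive) for x₁ = 5, 6, 7, 8, 9 are 0.0436 + 0.0344 + 0.0153 + 0.0038 + 0.0005, and the x₁ = 10 term is negligible. The unrounded sum is 0.0977. At p = 0.60, P(positive) = 0.8043. A full search confirms that 4/10 and 10/23 is the Simon optimal design for these inputs. The design arithmetic is right.

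**The same rule at the benchmark.** At p = 0.45 the terms for x₁ = 5 to 10 are 0.1341 + 0.1232 + 0.0677 + 0.0223 + 0.0041 + 0.0003. The unrounded sum is 0.3518.

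| True rate | Source | P(stop at stage 1) | P(positive) |
|---|---|---|---|
| 35% | null | 75.2% | 9.8% |
| 40% | assumption | 63.3% | 20.5% |
| 43.9% | untreated, Section 1.2.10 | 53.3% | 31.7% |
| 44.8% | first-line trial, Section 1.2.10 | 51.0% | 34.5% |
| 45% | benchmark, Section 10 | 50.4% | 35.2% |
| 50% | previously treated, Section 1.2.10 | 37.7% | 51.8% |
| 60% | target | 16.6% | 80.4% |

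**Which final counts exclude 45%?** Let s be the final number of responders. The one-sided 90% lower limit that accounts for stage 1 is the p that solves P(x₁ ≥ 5 and total ≥ s) = 0.10.

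| s of 23 | Observed | P(reaching s or more) at 45% | Lower limit |
|---|---|---|---|
| 10 | 43.5% | 42.5% | 32.4% |
| 11 | 47.8% | 35.2% | 35.1% |
| 12 | 52.2% | 25.8% | 38.3% |
| 13 | 56.5% | 16.3% | 41.9% |
| 14 | 60.9% | 8.8% | 45.7% |

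So 11/23 just excludes 35%, and 45% is excluded only from 14/23. Raising the threshold to 14 of 23 would cut power at 60% to 53.5%. The limit that ignores stage 1 (Clopper-Pearson, one-sided 90%) is 33.0% at 11/23. That lies below 35% and would contradict a result the rule calls positive, so the choice of interval matters.

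**What testing 45% would need.** For 45% versus 60% at the same alpha and beta, the Simon optimal design stops at 9 or fewer of 20 and needs 32 or more of 60 (alpha 0.098, power 0.804). The smallest two-stage design needs 51 patients.

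**The case against.** The strongest reply is that the 45% sentence is motivation and not a hypothesis. The formal null is stated plainly as 35% and restated with the early-termination probability. The primary objective in Section 1.1.1 is only to determine response, and Section 10 treats success as grounds for further study. On that reading 11/23 is a screening signal, and it is also the first count whose observed rate exceeds 45% (10/23 is 43.5%). This stands as a reason to keep the thresholds. It does not make the rule test 45%: 45% of 23 is 10.35, so 11 exceeds it by less than one patient.

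A null below 45% may also be reasonable, because eligibility mixes untreated and checkpoint-pretreated patients. No passage I could read makes that link. Section 1.2.11, on earlier experience with this combination in NSCLC, was not in the text available to me, so I do not claim that the plan lacks a rationale for 35%. Such a rationale would justify the null. It would not align the null with the 45% aim.

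The 50.0% rate belongs to previously treated patients who are not described as checkpoint-pretreated, so the 51.8% figure only illustrates how the rule behaves. The conclusion rests on the figures at 44.8% and 45%.

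Finally, the missing interval is wider than this cohort, and the decision rule works without one. That is true, but here the interval is what would show a reader which rate a given result excludes.

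**Conclusion.** The concern holds. The rule is a sound Simon design for 35% versus 60%, but Section 10 attaches to it an aim that it does not test. If the true rate equals the protocol's own benchmark, the cohort is called positive about one time in three (34.5% at 44.8%, 35.2% at 45%), compared with 9.8% at the 35% null. Results of 11, 12 or 13 of 23 are positive under the rule yet do not exclude 45% at one-sided 10%.

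These probabilities are exact binomial. They assume independent responses with one common rate, and the rule applied as written to 10 and then 23 evaluable patients. Reading 35% as a false-positive probability also assumes that the benchmark suits the enrolled mix. At an assumed 40% the figure is 20.5%. The wording should be corrected; the design need not be.

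**What to change.** Change the text and keep 5/10, 11/23 and N=23.

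1. **Section 10.** Replace the above-45% aim with wording such as: *This cohort is designed to rule out a response rate of 35% in favor of 60%. It is not designed to show a rate above the 45% reported for first-line pembrolizumab alone. At a true rate of 40%, 45% or 50%, the rule is met with probability 20.5%, 35.2% or 51.8%.* If there is a reason for choosing 35%, such as the mixed eligibility, state it here.
2. **Précis.** Say that a positive result means 35% is ruled out at one-sided 10% under the two-stage rule, and does not mean superiority to pembrolizumab alone.
3. **Section 10.1.** For this cohort, report the response rate with a one-sided 90% lower limit, or a two-sided 80% interval, that accounts for the two stages. It agrees with the rule: 32.4% at 10/23 (not positive), 35.1% at 11/23 (positive), and above 45% only from 14/23. A two-sided 95% interval may be added as description but should not be used to judge the rule, since even the stage-adjusted one is 28.5% to 74.5% at 11/23.

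This adds no patients and changes no threshold or stopping rule. The cost is a weaker claim: 11 to 13 of 23 could no longer be presented as exceeding the pembrolizumab-alone rate. Keeping the 45% aim as a tested claim would mean resizing the cohort, to 60 patients under the optimal design for 45% versus 60%.

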In a multi-institutional phase 1b trial, 25 previously treated MPM patients received pembrolizumab 10 mg/kg q2 weeks (99). Five (20%) patients experienced Grade 3 treatment-related adverse events. Three (12%) patients required dose interruption because of immune-related adverse events. No treatment-related deaths or discontinuations were observed. Five patients (20%) had a partial response; objective response: 20% (95% CI $6\cdot8-40\cdot7$); 13 patients (52%) had stable disease. The responses were durable (median response duration $12\cdot0$ months [95% CI $3\cdot7$ to not reached]). These preliminary findings demonstrated safety and potential efficacy of pembrolizumab in MPM patients.

In a subsequent study, Metaxas et al (100) reported results of 93 MPM patients who received pembrolizumab off-label in Switzerland and Australia. 48 patients (52%) received pembrolizumab as second-line treatment. 68 patients (73%) had epithelioid MPM, and 67 (72%) had an Eastern Cooperative Oncology Group performance status of 0 or 1. 66 of the 93 patients (71%) had PD-L1 expression analysis: 68% were negative, 18% were intermediate, and 14% had high intratumoral PD-L1 expression. The overall response rate (ORR) was 18%, with a median progression-free survival (mPFS) of 3.1 months (**Figure 24**); median overall survival was 7.2 months. ORR was 37%, mPFS was 3.7 months, and the median overall survival was 10.2 months in patients with ECOG PS of 0 or 1 and only one previous systemic treatment (n = 35), Patients with nonepitheloid histological subtype showed an improved ORR (24% versus 16% [p = 0.54) and mPFS (5.6 versus 2.8 months [p = 0.02]). Compared with intermediate and negative PD-L1 expression, high PD-L1 expression was associated with an improved ORR (44% versus 42% versus 11% [p = 0.01]) and mPFS (6.2 versus 3.9 versus 2.7 months [p = 0.04]). Toxicities in MPM patients were similar to those observed in patients with other malignancies.

[figure not shown]

Figure 24: Progression-free survival (PFS) and overall survival (OS) in the entire cohort. Kaplan-Meier curves of survival in the entire cohort (A), PFS according to line of treatment and performance status (PS) (B), and OS according to line of treatment and PS (C) (see the text).

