10 STATISTICAL CONSIDERATIONS

The primary objectives of this trial are to determine the objective response rates of DAC/THU plus pembrolizumab in patients with NSCLC, EsC, and MPM who have intra-tumoral PD-L1 expression of at least 50% and those who do not. Approximately 30% of NSCLC exhibit PD-L1 expression in 50% or more cancers cells, another 30-50% have PD-L1 expression in 1-49% of cancer cells, and the remaining NSCLC have no PD-L1 expression by IHC (25, 111-113). In contrast, 20-40% of gastroesophageal cancers exhibit PD-L1 expression (25, 111, 112); in the majority of these cancers, PD-L1 is expressed at low levels, and tends not to be expressed on the cancer cells (112). Despite these differences regarding PD-L1 expression, present data indicate that responses to immune checkpoint inhibitors in EsC are comparable to NSCLC with low PD-L1 expression (114). Approximately 25%-30% of MPM exhibit some level of PD-L1 expression, with the expression being primarily on tumor-associated immune cells (115). PD-L1 expression tends to be higher on sarcomatoid MPM and lower on the more common epithelioid subtype. Response rates in MPM following PD-1 blockade are comparable to NSCLC with similar levels of PD-L1 expression (99, 100).

Patients will be initially enrolled onto a multi-dose level dose escalation portion of the trial following a 3+3 design. Patients will not be stratified for the Phase I component, which will accelerate our ability to define MTD. Thus, for the dose escalation phase, up to 6 patients per dose level may be enrolled, with a total of 12 patients required with a maximum of 2 dose levels. At the MTD, an additional 4 patients will be enrolled to further estimate the safety of the combination.

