NSCLC patients with low (0-49%) intratumoral PD-L1 expression will be evaluated for response using a Simon optimal two-stage Phase II trial design (116) in order to rule out an unacceptably low PR+CR rate of 10% (p0=0.10) in favor of an improved response rate of 30% (p1=0.30). Variable mutational burdens among NSCLC with low PD-L1 expression could affect responses to immune checkpoint inhibitors, potentially making this cohort more heterogeneous than the NSCLC high PD-L1 expresser cohort. For example, NSCLC patients without activating mutations in EGFR, HER2 or ALK with PD-L1 tumor proportion score (TPS) < 1% have an expected response rate of less than 10%, whereas those with activating mutations involving these genes have response rates of 5% or less; patients with PD-L1 TPS of 1-49% have a 17% response rate (25, 103, 104, 113). Therefore, with alpha=0.05 (probability of accepting a poor treatment=0.05) and beta = 0.20 (probability of rejecting a good treatment=0.20), the first stage will determine the response rate in 10 evaluable patients, including those among the 10 who are treated at the MTD from the Phase I cohort who have low intra-tumoral PD-L1 expression, and if 0 to 1 of the 10 have a clinical response, then no further patients will be accrued. If 2 or more of these 10 patients have a response, then accrual would continue until a total of 29 evaluable patients have been treated in this cohort. As it may take up to several months to determine if a patient has experienced a response, a temporary pause in the accrual may be necessary to ensure that enrollment to the second stage is warranted. If there are 2 to 5 patients with a response out of 29 patients, this would be an uninterestingly low response rate. If there were 6 or more of 29 (20.7%) who experienced a response, this would be sufficiently interesting to warrant further study in later trials. Under the null hypothesis (10% response rate), the probability of early termination is 73.6%.

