While accrual of NSCLC patients is underway, up to 10 EsC patients including any from the Phase I component after the MTD has been identified, will be accrued to examine responses in EsC patients treated with DAC-THU at the MTD and pembrolizumab. Since it is anticipated that most if not all of these 10 patients will have low or no PD-L1 expression in their tumor tissues, and because response rates to immune checkpoint inhibitors in EsC appear to be comparable to NSCLC with low PD-L1 expression, criteria similar to those reported for the NSCLC low PD-L1 cohort

will be used to identify a potential signal of activity. Specifically, if there are 2 or more responses in these 10 patients, this might warrant amendment of the current protocol to enable expansion of this cohort with appropriate statistical criteria, or to justify a larger, focused Phase II trial.

Additionally, up to 10 MPM patients including any from the Phase I component after the MTD has been identified, will be accrued to examine responses in MPM patients treated with DAC-THU at the MTD and pembrolizumab. Since it is anticipated that most if not all of these 10 patients will have low PD-L1 expression in their tumor tissues, and because response rates to immune checkpoint inhibitors in MPM patients appear to be comparable to NSCLC with low PD-L1 expression, criteria similar to those reported for the NSCLC low PD-L1 cohort will be used to identify a potential signal of activity. Specifically, if there are 2 or more responses in these 10 patients, this might warrant amendment of the current protocol to enable expansion of this cohort with appropriate statistical criteria, or to justify a larger, focused Phase II trial.

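### The MPM signal of 2 or more responses in 10 inherits a 10% benchmark, but the protocol's own rates for pembrolizumab alone in MPM are 18–22%, at which the rule is met 56–68% of the time with no DAC-THU effect

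*Combined protocol and SAP*

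**What the plan says.** Section 10 enrols up to 10 MPM patients at the MTD and treats 2 or more responses as a possible sign of activity. The Précis and Section 3.1 repeat the rule. Section 10 gives two reasons for using criteria like those of the low PD-L1 NSCLC cohort. Most or all of the 10 patients are expected to have low PD-L1, and the criteria carry over "because response rates to immune checkpoint inhibitors in MPM patients appear to be comparable to NSCLC with low PD-L1 expression".

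The NSCLC design being borrowed aims to "rule out an unacceptably low PR+CR rate of 10% (p0=0.10") against a target of 30%. It stops after 10 patients if there are 0 or 1 responses, and otherwise continues to 29 patients, where at least 6 responses are needed. Its early-termination probability at 10% is given as 73.6%.

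Earlier in Section 10 the comparability claim is narrower: "Response rates in MPM following PD-1 blockade are comparable to NSCLC with similar levels of PD-L1 expression (99, 100"). Section 2.1.1.6.5 sets no PD-L1 restriction for Cohort 5.

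The consequence of a positive signal is worded softly: "this might warrant amendment of the current protocol to enable expansion of this cohort with appropriate statistical criteria", or it may justify a larger Phase II trial. Section 10 gives no null rate, target rate or operating characteristic for the MPM rule itself.

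**The concern.** A 2-of-10 gate makes sense when the background rate is near 10%, because two responses are then twice what the comparator would be expected to give. At a background of 20%, two responses in ten are simply the expected number on pembrolizumab alone. The protocol's own literature summary puts MPM near 20%, so the benchmark behind the rule conflicts with the data cited elsewhere in the same document.

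Two features make this matter more for MPM than for the NSCLC cohort. First, the NSCLC gate is backed by a second stage with stated error rates, while the MPM cohort has only the gate. Second, response in MPM is part of the Phase II primary objective (Section 1.1.1), and 2 of 10 is the only criterion offered for it. An amendment or a new trial could follow from a result that pembrolizumab alone would be expected to give.

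**Working it through.** **Inputs**
- Rule: at least 2 responses in n = 10 (Section 10).
- Borrowed design: p0 = 10%, p1 = 30%, stages of 10 and 29 patients (Section 10).
- MPM on pembrolizumab alone (Section 1.2.10):
  - 25-patient phase 1b trial: "Five patients (20%) had a partial response", with 95% CI 6.8–40.7%.
  - 93-patient off-label series: "The overall response rate (ORR) was 18%, with a median progression-free survival".
  - Pembrolizumab arm (n = 73) of the randomised Phase III trial: 22%.
- Subgroups of the 93-patient series: 11% PD-L1 negative, 42% intermediate, 44% high. The 66 tested patients were 68% negative, 18% intermediate and 14% high. For the 35 fitter patients with a single earlier line of therapy, the section reports: "ORR was 37%, mPFS was 3.7 months, and the median overall survival was 10.2 months in patients with ECOG PS of 0 or 1".
- NSCLC comparison point in Section 10: "patients with PD-L1 TPS of 1-49% have a 17% response rate".

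**Formula.** With true response rate p, P(at least 2 of 10) = 1 − (1−p)^10 − 10p(1−p)^9.

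**Step 1: reproduce the plan's figure.** At p = 0.10, 0.9^10 = 0.3487 and 10 × 0.1 × 0.9^9 = 0.3874. These sum to 0.736, the stated 73.6% early-termination probability. Summing over both stages gives alpha 0.047 and power 0.805, so the NSCLC design is correct in its own setting. The gate is passed 26.4% of the time at 10%.

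**Step 2: apply the same formula at MPM rates, with no DAC-THU effect.** At p = 0.20, for example, 0.8^10 = 0.1074 and 10 × 0.2 × 0.8^9 = 0.2684, so the result is 1 − 0.3758 = 0.624.

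| Background rate | Source | P(at least 2 of 10) |
|---|---|---|
| 10% | borrowed NSCLC p0 | 26% |
| 11% | MPM, PD-L1 negative | 30% |
| 17% | NSCLC, PD-L1 1–49% | 53% |
| 17.5% | MPM, negative plus intermediate | 54% |
| 18% | MPM, 93-patient series | 56% |
| 20% | MPM, 25-patient trial | 62% |
| 22% | MPM, Phase III arm | 68% |
| 37% | MPM, ECOG 0–1 with one prior treatment | 93% |

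The 17.5% is (0.68 × 11% + 0.18 × 42%) / 0.86. It assumes that intermediate expression lies within 0–49%, which the protocol does not define.

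The probability passes one half between a background of 16% (49%) and 17% (53%).

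**Step 3: how uncertain the background is.** The confidence limits of the 25-patient trial alone (6.8% and 40.7%) give 14% and 96%. A low figure of about 7% can be rebuilt: 18% of 93 is about 17 responders and 37% of 35 is about 13, which leaves about 4 of 58 (6.9%, exact 95% CI 1.9–16.7%). The rule is then met 15% of the time. No study reports this rate. It comes from rounded percentages and should be labelled an assumption.

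**Step 4: a higher threshold, for information.** At least 3 of 10 is met 32% of the time at 20%. At a true rate of 30%, the chance of a signal falls from 85% (at least 2) to 62% (at least 3).

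**The case against.** The strongest reply is that the rule claims little. It flags possible activity, says only that expansion might be warranted, and requires any expansion of this cohort to carry its own statistical criteria. That is correct and limits the harm. A reader might infer from the percentages that the plan breaches a type I error rate, or that it treats 2 of 10 as proof that DAC-THU works. The documents support neither reading: no alpha is stated for MPM, and no section says that 2 of 10 isolates a DAC-THU effect. It is also true that Section 10 prints no 10% for MPM; that figure is inherited from the NSCLC design.

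A second reply is that low PD-L1 expression is expected. Section 10 says that about 25–30% of MPM express any PD-L1, mainly on immune cells. The PD-L1-negative rate of 11% is close to the rate of under 10% given for NSCLC with TPS below 1%. This stands for PD-L1-negative patients only. Enrolment is not restricted to them, and adding the intermediate group brings the background to about 17.5%.

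A third reply is that the background in Cohort 5 is unknown. It admits ECOG up to 2, as well as treated patients and those who refused or were ineligible for chemotherapy. This also stands. It is a reason to print a range with low and high subgroups alike, and not to rely on one borrowed figure.

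**Conclusion.** The point holds as a mismatch between the MPM rule and the protocol's own data. At the three overall MPM rates (18–22%), pembrolizumab alone would meet the rule 56–68% of the time, against 26% at the inherited 10%. The arithmetic is exact. What is uncertain is which background applies to Cohort 5: the reported subgroup rates run from 11% (30%) to 37% (93%).

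A reader might go further and conclude that the false-go probability in this cohort is above one half. That follows only if the background exceeds about 16%. The three overall rates do, but the PD-L1-negative rate does not, and the cohort's mix is not known in advance. Nor do the documents show that the threshold of 2 is wrong. For a 10-patient screen, the balance between a false go and a missed signal is for the sponsor to choose.

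The calculation assumes independent responses, 10 evaluable patients, and historical rates that carry over to this population. The three studies are not pooled because dose, schedule and setting differ.

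**What to change.** In the MPM paragraph of Section 10, with matching text in the Précis and Section 3.1:

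1. Replace the inherited low PD-L1 NSCLC benchmark with an explicit MPM reference rate drawn from Section 1.2.10 (overall, about 18–22%).
2. State the probability of meeting 2 or more of 10 across a balanced background range: 26% at 10%, 30% at 11%, 56% at 18%, 62% at 20%, 68% at 22% and 93% at 37%. State it also at a target rate the sponsor names, since the protocol gives none for MPM. If a 7% background is shown (15%), label it an assumption rebuilt from rounded counts.
3. State that 2 of 10 would show activity of the combination consistent with pembrolizumab alone, and is not by itself evidence that DAC-THU adds activity.

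All three are wording changes. The threshold, the cohort size, and the EsC and NSCLC rules need not change. Raising the signal to 3 of 10 is the sponsor's trade-off and not part of this fix: it leaves a 32% false-go probability at 20% and lowers the chance of a signal at a true 30% from 85% to 62%.
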